1. INTRODUCTION

POTIGA was approved with a FDA requirement for a Risk Evaluation and Mitigation Strategy (REMS). The goal of the REMS for POTIGA is to inform healthcare professionals of the risk of urinary retention and the symptoms of acute urinary retention in patients taking POTIGA. The REMS is comprised of a communication plan for healthcare professionals that is designed to disseminate information about the risk of urinary retention with POTIGA and highlight this potential risk and the need to inform patients to seek immediate medical attention for symptoms of urinary retention, inability to urinate, and/or pain with urination. There are two elements of the communication plan: (1) A Dear Healthcare Professional (HCP) Letter designed to disseminate information about the risk of urinary retention with POTIGA; letters are disseminated within 4 weeks of first retail availability (actual – May 7, 2012) and annually for the next two years (2) a REMS Program Website (available at time of launch; actual -April 16, 2012).

The target audience for these communications is: (1) Prescribing physicians i.e., Epileptologists, Neurologists and Neurosurgeons, (2) Pharmacists dispensing POTIGA tablets and the Medication Guide.

As a condition of approval, FDA requires that GlaxoSmithKline (GSK) assess the effectiveness of the communication plan. Accordingly, a survey will be conducted among a sample of prescribing physicians to evaluate whether they can recall the risk of urinary retention with POTIGA. In addition, the survey will evaluate where HCPs prefer to seek information for POTIGA, for example Dear HCP letters, website, or product labeling. The survey will concentrate on the risks described in the DHCP letter for POTIGA, though it is recognised that the DHCP letter is not the only source of information concerning risks associated with medication use. The design for this study is based on previous experience of risk management programs for GSK products.

A survey will also be conducted among a sample of pharmacists to evaluate whether they can recall the risk of urinary retention with POTIGA.

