I don't know/don't remember	7

27. Approximately how many patients have you dispensed POTIGA for in the past 12 months?

ALLOW ONE RESPONSE.

1-2	1
3-10	2
11-20	3
More than 20 patients	4
I don't know/don't remember	5

28. On a monthly basis, approximately how many prescriptions for anti-epileptic drugs (AEDs) (including new prescriptions and refills) have you filled in the past 12 months?

ALLOW ONE RESPONSE.

1 – 10	1
11 – 30	2
31 – 50	3
More than 50 prescriptions	4

SECTION C: The remaining questions are about your own personal experience, specifically regarding your awareness, receipt and dissemination of information about POTIGA.

29. Have you learned about the risks associated with use of POTIGA from any of the following sources?

	Yes	No	Don't
POTIGA Dear HCP Letter	1	2	3
GlaxoSmithKline Medical Information	1	2	3
Other Healthcare Professionals	1	2	3
GlaxoSmithKline Promotional Materials	1	2	3
GSK Website: POTIGA.com	1	2	3
GlaxoSmithKline Sales Representatives	1	2	3
GlaxoSmithKline-sponsored Educational Meeting	1	2	3
POTIGA Product Labeling (including Prescribing Information, Medication Guide)	1	2	3

30. How would you prefer to learn about the risks associated with use of POTIGA in the future? Please select up to 3 options.

POTIGA Dear HCP Letter	
GlaxoSmithKline Medical Information	
Other Healthcare Professionals	
GlaxoSmithKline Promotional Materials	
GSK Website: POTIGA.com	
GlaxoSmithKline Sales Representatives	
GlaxoSmithKline-sponsored Educational Meeting	
POTIGA Product Labeling (including Prescribing Information, Medication Guide)	

CLOSING: Those are all of our questions. Thank you very much for your time and for sharing your responses with us today. As you may know, medication manufacturers conduct surveys, such as this one, from time to time to learn how well they have communicated to healthcare providers regarding the risks that may be associated with that medication.

We would now like for you to take a moment to review some important information about POTIGA. This information can be found in the Prescribing Information, which can be found online at:
http://us.gsk.com/products/assets/us_potiga.pdf

The Dear Healthcare Professional Letters (for prescribing physicians and pharmacists) can be found online at:

Prescribing Physicians:

https://www.gsksource.com/gskprm/en/US/images/gsk_content/POTIGA/PGA056R0_RMS_HCP_Letter_DC.pdf

Pharmacists:

https://www.gsksource.com/gskprm/en/US/images/gsk_content/POTIGA/PGA055R0_RMS_PharmLetter_DC.pdf

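### Q29 and Q30 are closed lists of the same eight, mostly sponsor, sources: neither has an Other (specify) row and Q30 has no No-preference option, so unlisted sources go unrecorded and a blank in Q30 is ambiguous

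*Protocol*

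**What the plan says.** Protocol Section 1 (Introduction) sets a task beyond the knowledge questions: "the survey will evaluate where HCPs prefer to seek information for POTIGA, for example Dear HCP letters, website, or product labeling". It also grants that "it is recognised that the DHCP letter is not the only source of information concerning risks associated with medication use".

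Two items in Section 11.2, Section C, carry this subject, and all respondents are routed to them.

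- Q29 asks "Have you learned about the risks associated with use of POTIGA from any of the following sources". It is a grid in which each source gets its own Yes, No or Don't answer (the last column read here as don't know).
- Q30 asks "How would you prefer to learn about the risks associated with use of POTIGA in the future? Please select up to 3 options". It is a pick list of the same sources, with no stated minimum number of choices.

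The eight sources include "POTIGA Dear HCP Letter", "GlaxoSmithKline Medical Information", "GlaxoSmithKline Promotional Materials" and "Other Healthcare Professionals". The other four are the product website, the sponsor's sales representatives, a sponsored educational meeting and product labeling.

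**The concern.** Section 1 asks where HCPs prefer to look, and it names letters, website and labeling only as examples. A closed list answers a narrower question: which of these eight do they prefer? Someone whose preferred source is, say, a drug reference, a journal or independent education has two choices in Q30: tick something listed or leave the item empty. The first enters the table as a preference for a listed source; the second cannot be interpreted.

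Q29 has a milder form of the same gap. A respondent who learned of the risk only from an unlisted source answers No on every row, exactly as does one who learned of it from no source.

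At stake is how far these two tables can guide later risk communication. If the Q30 ranking is read as HCPs' preferences in general, part of it reflects the composition of the list.

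**Working it through.** There is no sample size or error rate to reproduce. The check is a count of options and a reading of the answer formats against the stated aim.

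**1. Count of options (Section 11.2, Q29 and Q30; identical lists)**

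| Type of source | Options | Count |
|---|---|---|
| Sponsor communication | letter, medical information, promotional materials, website, sales representatives, sponsored meeting | 6 |
| Approved labeling | product labeling, including prescribing information and Medication Guide | 1 |
| Not from the sponsor | other healthcare professionals | 1 |
| Total | | 8 |

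Sponsor share with labeling counted: 7/8 = 87.5%. Without labeling: 6/8 = 75%. Non-sponsor share: 1/8 = 12.5%. Section 3.3.1 places the Medication Guide within FDA-approved labeling, so either count can be defended.

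**2. Exits from the list**

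| | Q29 | Q30 |
|---|---|---|
| Other (specify) | absent | absent |
| None or No preference | no row, but No on all eight rows records it | absent |
| Don't know | a column for each row | absent |
| Blank accepted? | not stated | not stated |

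Whatever share of HCPs prefers or used an unlisted source, the number recorded for that source is 0 by construction. In Q30 a blank has at least three possible meanings (no preference, unlisted preference, nonresponse), and nothing in the item separates them.

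**3. Does another part of the survey fill the gap?**

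- Section B of the questionnaire takes free text, but it is optional, appears only after incorrect answers to Q1–Q13, and asks why that answer was chosen. A respondent with every answer correct never sees it.
- Section 3.1 gives the telephone and online modes the same response options and bars interviewers from departing from the procedure. An interviewer therefore has no row for a source volunteered by the respondent.

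**4. Comparison with the rest of the instrument**

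The specialty items (screener Q3 and questionnaire QA) have an Other (Specify) line. Most select-all knowledge items end with a none-of-the-above and a don't-know option. Q30 has neither kind of exit.

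**5. Who is asked**

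Under Section 4.2.1 a pharmacist qualifies by filling any AED prescription in the previous three months. Q25 allows No to having dispensed POTIGA, and those pharmacists still go on to Section C. For them it is plausible, though the document cannot show it, that information came from outside the sponsor's channels.

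**6. What depends on Q29 and Q30**

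The two objectives in Section 2 concern understanding of the risk and its symptoms. The primary outcome in Sections 5.2 and 7.2 is the proportion correct for each risk question, and the 80% threshold applies to those questions. None of these uses Q29 or Q30. Source of learning is also not among the subgroups named in Section 7.2.

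**The case against.** The best defence is that the list fits its purpose. The REMS communication plan consists of a letter and a website, and the survey assesses that plan. All three examples in Section 1 are offered. Preference is not an objective in Section 2, and the study is descriptive with no formal testing. Which further sources to name is partly a matter of taste, and changing a questionnaire already in the field splits the tables.

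Much of this stands. It limits the point to a minor one and argues against a long list of new categories. It does not remove the gap, because Section 1 states the preference aim in general terms and Q30 is the item that asks about it.

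A reader might infer more than the document supports:

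- *That the survey cannot show where HCPs learned or prefer to learn.* It can for the listed sources. Q29 gives the share who learned from each, including the letter, and Q30 gives relative preference among the eight.
- *That only sponsor channels can be returned.* Other healthcare professionals is a non-sponsor option in both lists.
- *That Q29 needs a None row.* The row-by-row format already records it.
- *That the knowledge results are compromised, because people taught by unlisted sources look informed but unexposed.* Such a respondent would have to answer No on all eight rows, labeling and colleagues included. The Protocol plans no named analysis of percent correct by source and does not claim that the letter explains the percentages.
- *That a particular number of respondents is affected.* The document gives no share from which to compute one. Q30 also allows up to three choices, so a respondent with one unlisted preference can still record listed ones.

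**Conclusion.** The point holds in a limited form. Q29 and Q30 cannot record any source outside the eight. Q30 therefore measures preference only within a list that is 75% or 87.5% sponsor-originated, depending on how labeling is classed, and a blank in Q30 has no single meaning. This falls short of the broader question that Section 1 sets.

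The number of respondents affected is unknown and cannot be estimated from the Protocol. The conclusion assumes that the printed questionnaire is complete, with no write-in field or forced-response rule programmed elsewhere. The consequence is restricted to two non-primary descriptive tables; the per-question proportions correct and their comparison with 80% stand as they are. It is a minor matter, worth correcting because the correction is cheap.

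**What to change.** 1. Add an Other (specify) row to Q29 and to Q30.
2. Add a No-preference option to Q30 that excludes the other choices. No None row is needed in Q29.
3. Make the same change in the online and telephone scripts, as Section 3.1 requires identical options. Section 5.2 randomizes response order, so keep the new rows at the end of each list.
4. Report the Q29 and Q30 tables by questionnaire version. For respondents who saw the present lists, state that results are restricted to the listed sources and report blanks in Q30 as a separate count.

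If the sponsor prefers not to alter the instrument during this wave, the restriction statement and the count of blanks should still go into the report, and the new rows can be used at a later assessment; Section 1 describes this one as the first.

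The cost is three answer lines, coding of a short free-text field, and a by-version split of two descriptive tables. Sections 3.2 and 5.1 show that the honorarium and the screener were changed after the start, so a mid-study amendment has precedent. No knowledge question, sample size or threshold changes.

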11.3. GlaxoSmithKline Adverse Drug Reaction Form – Revised Nov 30, 2009

Global Adverse Event Report Reporting Form for Marketing Research	

To be completed by Market Research Agency – this form applies to both patients and HCPs. This form is to be used for AEs mentioned worldwide in market research commissioned by GSK global. Minimum criteria - A Reporter, at least one patient detail, suspect drug and adverse event Please complete with as much detail as possible and forward within one business day (24 hours) to your Pharmaceutical company contact via fax to:
	
For drugs	GSK Case Management Group Reports from Americas: [contact] (US fax #) Reports outside of Americas: [contact] (UK fax #) Reports from US & Canada: [contact] (US fax #) Reports outside US & Canada: [contact] (Belgium fax #)
For vaccines	GSK Biologicals Case Management Group
Market Research Agency:	Date aware of the adverse event/product complaint: Month: Date: Year:
Agency Address (include country):	Project Title and Agency Reference/Project No:
Agency Telephone No:	Researchers Name:
Agency Fax No:	Researchers Signature:
Drug(s)/ Vaccine(s) and Event(s) Details	
Drug/ Vaccines Name(s):	Adverse Event(s)/Product Complaint details:
Indication (condition for which the drug(s)/ vaccine(s) has been prescribed):	
Unknown  Was the patient pregnant? Yes  No  Unknown 	Reported to the local regulatory agency? Yes  No  Unknown  Lot/Batch number: 
Unknown 

Dose: Unknown 	Did the HCP/patient consider that the event was possibly related to the drug/ vaccine? Yes  No  Unknown 
Patient Details (At least one of these patient details MUST be completed)	
Age:	Other (approx. age of patient)
Sex: Male  Female 	
Respondent Details	
If consent not given to disclose personal details, just complete the type of reporter (i.e., Dr., nurse, patient, pharm.)	
Respondent name:	Doctor 
Address:	Nurse 
Telephone No:	Patient 
Email:	Pharmacist 
Is respondent willing for the Pharmaceutical company's safety team to contact them or their doctor to discuss further? Yes  No 	Respondent Signature:
